- Regularly eats a breakfast meal before midday
- Access to internet and email

Exclusion criteria

- Prescribed anti-hyperglycaemia agents *i.e.* Glucophage (Metformin) and or antidepressants.
- Any other medical conditions that may impact on the digestion and or absorption of nutrients, including coeliac disease and gastroparesis.
- Vegans
- Allergic or intolerant to the test meals
- Experiencing difficulties with food including diagnosed eating disorders
- Currently actively taking part in another research study

Recruitment

Paediatric diabetes dietitians, working across the UK, will be enrolled to help recruit participants and become principal investigators (PI) for their site. On enrolment, the chief investigator will provide the dietitians with all the relevant participant information sheets and consent forms as well as an Excel spreadsheet for entering the baseline information. The study documentation is presented in Appendices 1-9.

Sample size

The sample size power calculation is 64. This is based on using ANOVA repeated measures, within factors with four groups and measurements (3 test meals and control) with small effect size (0.15), P value 0.05 and power 0.80 and correlation among repeated measure of 0.5. The drop rate of clinical trials is often over 40%. Therefore, the aim is to recruit 90 participants to allow for this dropout rate and meet the sample size of 64. It may be possible to recruit this number of participants. There are approximately 29,000 children and young people living in the UK with T1D (Juvenile Diabetes Research Federation (JDRF), 2018). In the first phase of this study, 12 NHS sites were enrolled, and 96 children and young people were recruited to the study.

Methodology

Baseline data

In order to make comparisons between relevant variables and glucose levels, the following baseline data will be collected from the dietitians and sent to the chief investigator, along with the artificial identifier on the Excel spreadsheet as discussed earlier at the stage of recruitment of participants:

- Parent's email address
- Sex, date of birth and recent weight and height (for calculation of BMI and BMI centile) and date of when this was taken
- Date of diagnosis of T1D
- Last four HbA1c
- Total daily insulin dose (TDD)
- Insulin: carbohydrate ratios (ICR) and Insulin Sensitivity Factor (ISF)

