- Current insulin regimen - including the type of insulin prescribed and if applicable type of insulin pump i.e. open or closed loop system.

Run-in period

At recruitment the dietitians will be asked to arrange a review of the participants insulin regimen including the insulin to carbohydrate ratio's (ICR), insulin sensitivity factor (ISF) and basal background insulin doses/rates. The dietitian will be asked to inform the chief investigator when this has taken place. Participants will be asked to commence the test meals following this.

Glucose measurement

Data on interstitial glucose will be collected via Dexcom CGM. The Dexcom CGM data will be accessed by an NHS Highland research 'Clarity Clinic' with Dexcom CLARITY® Clinic Portal (Dexcom In, San Diego, CA, USA). The chief investigator is administrator of this clinic. Once the managing dietitian has obtained each participant's consent, the participant's parent's email address will be sent to the chief investigator along with the baseline information/data as described above. The chief investigator, as administrator of the Clarity Clinic account, will then invite the participant, via email, to be added to the clinic. Once the invite has been accepted, it will stand for the period of the recording i.e. until all the test meals and questionnaires have been completed. Once the participant has submitted their last questionnaire, they will be removed from the Dexcom CLARITY® Clinic Portal. They will be removed from the clinic portal if they withdraw from the study.

Test and control meals

Following the provision of CGM data and review of the insulin regimen by the diabetes team, participants will be randomised to test each of the three test meals on two separate occasions with a control meal (usual breakfast meal) for each test meal. Randomisation will be achieved using a Latin square randomisation. The tool used for this will be <http://www.jerrydallal.com/random/randomize.htm>. Randomisation will be done in a block of four.

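### Insulin dose and sensitivity values for the third objective may be recorded, undated, before the review that can change them, and the plan requests no values after that review

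*Combined protocol and SAP*

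**What the plan says.** The third item under Objectives compares the glucose measures with participant variables, among them insulin dose/sensitivity. Baseline data gives the purpose of the collected items: "In order to make comparisons between relevant variables and glucose levels, the following baseline data will be collected from the dietitians". The list includes TDD, ICR and ISF. These are therefore analysis variables as well as cohort description, and Expected outcomes likewise draws the comparison variables from the baseline information.

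On timing, Baseline data says the items go to the chief investigator "along with the artificial identifier on the Excel spreadsheet as discussed earlier at the stage of recruitment of participants". Glucose measurement says that, after consent, the parent's "email address will be sent to the chief investigator along with the baseline information/data as described above". The data-management text on baseline information adds that the values come from clinical records. The list asks for "recent weight and height (for calculation of BMI and BMI centile) and date of when this was taken"; it asks for no date for TDD, ICR or ISF.

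On the review, Run-in period says: "At recruitment the dietitians will be asked to arrange a review of the participants insulin regimen", and names ICR, ISF and basal doses or rates as its content. The Project summary and Burden on dietitians describe the aim as optimising insulin before the meals. The follow-up is: "The dietitian will be asked to inform the chief investigator when this has taken place". Test and control meals then states: "Following the provision of CGM data and review of the insulin regimen by the diabetes team, participants will be randomised".

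**The concern.** A covariate meant to help explain glucose after breakfast should describe the insulin settings in use at that breakfast. Here the plan places a review, whose purpose is to adjust those settings, between recruitment and the meals. It asks for the settings at recruitment and only for notice of completion afterwards. For a child whose ICR or ISF changed at the review, the recorded value could be the superseded one. TDD is exposed as well, since it is the sum of doses that the review may alter. With no date on these entries, the analyst could not tell which children are affected, and the answer might differ between sites.

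At stake is one group of covariates in one descriptive objective.

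**Working it through.** The plan states no figure on this point, so the check sets the sections side by side.

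1. **Are the values used in analysis?** Yes. Objectives names insulin dose/sensitivity, Baseline data says the items are collected for comparison with glucose, and Expected outcomes points to baseline information as the source.

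2. **When are they sent?** Glucose measurement ties sending to consent and to the email address needed for the Clarity invitation. It does not tie sending to the review.

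3. **When is the review?** It is arranged at recruitment and finished before the meals, and its completion is notified separately. A separate notice suggests that the review and the sending of baseline data are different events. That is an inference from the text.

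4. **Does the review cover the same quantities?** ICR and ISF appear both in the baseline list and in the content of the review. TDD is not named in the review, but it depends on basal and mealtime doses.

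5. **Which settings apply at the meals?** The reviewed ones, because randomisation to the meals follows the review and participants then use the regimen advised by their team.

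6. **Are post-review values requested?** Not in the sections available. Run-in period asks only for notice that the review has happened.

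7. **Could the analyst tell the order afterwards?** Not from the listed items. A date is asked for with weight and height, but not with TDD, ICR or ISF.

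8. **Does this reach the primary analysis?** No. The primary outcome is mean glucose over the three hours after breakfast, compared across meals within the same child, and it does not use these covariates. The sample size of 64 rests on an effect size of 0.15, a P value of 0.05, power of 0.80, a correlation of 0.5 and four repeated measurements. None of these depends on insulin settings.

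9. **How large is the effect?** It cannot be calculated. It depends on how many children have settings changed, by how much, and whether the change is related to the earlier value. The documents give none of these.

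**The case against.** The strongest reply is that the order is not stated. In the Baseline data sentence, the words about recruitment may belong to the back-reference rather than to the time of collection. Consent sets the earliest time for sending the data, not a deadline before the review. One visit could serve for both, and if the sheet is completed after the review there is no mismatch. This stands: a reader might infer that the recorded values are known to predate the review, and the documents do not establish that. The timing is simply left open, and a date would settle it.

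Second, the forms themselves are not available. The plan mentions "an Excel spreadsheet for entering the baseline information" and a postprandial questionnaire in Appendix 10 that asks about diabetes management. Either could hold dates or doses. It would be wrong to conclude that they do not, or that dietitians would send nothing beyond the notice. What can be said is that the body of the plan does not ask for it.

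Third, using baseline values as baseline covariates is what the plan says, and HbA1c and BMI also precede the meals. But the study does not schedule a step to adjust HbA1c or BMI between collection and the meals, as it does for insulin settings.

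Fourth, the review is presented as usual care, so few settings may change. That is possible. It limits the likely size, but a review whose purpose is to optimise must allow for change.

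Finally, a reader might infer that the values would be lost for good. The plan keeps artificial identifiers until 6-12 months after the study ends, so a later query to sites looks feasible, though none is planned.

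**Conclusion.** The point holds as a minor, conditional one. Followed as written, the plan can supply the third objective with ICR, ISF and TDD values that were superseded before the meals, and it gives the analyst no stated means of noticing. This rests on two assumptions: that at least some sheets are completed before the review, and that no form outside the available text already records the later values. Both are plausible and neither is confirmed. The size is unknown.

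A reader might go further and infer bias in the meal comparison or a loss of power. The documents support neither: the meal comparison is within participant and does not use these values, and the third objective is descriptive and was not the basis of the sample size.

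**What to change.** With the notice that the review has taken place, have the dietitian send dated post-review ICR and ISF, or confirm that nothing changed. Add a dated TDD recorded after the review and before the first test meal, where one is available. The window should close before the first meal because a TDD from the meal days could include insulin given in response to the glucose being analysed.

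State that the third objective uses these values, keep the recruitment values to describe the cohort, and report how many children had settings changed. If sites complete the sheet after the review, a date on each entry is enough. If the spreadsheet or Appendix 10 already records the values, naming it as the source is enough.

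The cost is a few extra fields per participant on a notice that is already sent, with no extra visit. Where a colleague in the diabetes team carries out the review, as Burden on dietitians allows, the dietitian would have to obtain the values from them. Post-review TDD may be missing for some children.

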Project summary

Type 1 diabetes (T1D) is a chronic disease which requires daily calculations of food intake and insulin dose adjustment to achieve good glycaemic control and minimise the risk of developing diabetic complications. However, even when glycaemic control appears to be good, as demonstrated by average glycated haemoglobin (HbA1c), children and young people with T1D frequently experience glucose variability, with levels above and below the target range. The main cause of diurnal glucose variability is food intake, which can cause postprandial hyperglycaemia. Postprandial hyperglycemia can occur after any meal, although there is some evidence that it may be worse after breakfast. There is limited data on the occurrence and cause of this and its association with different variables, including food composition and the glycaemic load of a meal.

Methods:

This project will be a quantitative study. The study proposes to recruit 90 children and young people who have T1D and who regularly use Dexcom continuous glucose monitoring (CGM). Recruitment will be via their managing dietitian. The dietitian will be asked to provide baseline information about the participants which will include demographic data and information on clinical data, treatment and anthropometrics. Participants will be asked to provide access to Dexcom CGM data throughout the period of recording. Participants will be asked to test three breakfast meals (high glycaemic load, high glycaemic with 10g added protein and medium glycaemic load) plus a control meal (usual breakfast), repeating each meal twice in a randomized order using a Latin square randomisation. The dietitian will be asked to optimise the participants insulin doses prior to commencing test meals. Participants will be asked to complete a questionnaire for each of the postprandial test and control meal periods. This will include questions about their diabetes management, food and fluid intake in addition to questions on activities all of which took place during the three-hour postprandial period. The glycaemic response to the test and control meals will be analysed using the CGM data and the results statistically described using univariate, bivariate and multivariate analysis.

Study protocol

Full Study Title:

The Breakfast Rise, Education and Knowledge Study in Children and Young People who have Type 1 Diabetes (T1D): The BREAK study.

Short title

The BREAK study.

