The test meals are based on foods children and young people enjoy eating. There are three meals. Test meal one includes a high glycaemic index cereal meal with milk and has a high glycaemic load (> 20), test meal two is the same cereal meal with a high glycaemic load (>20) with addition of 10g protein and test meal three has a medium glycaemic load (10-20). For test meals one and two there are three portion size options to meet age appropriate requirements and appetites. The participants will be able to choose from two different cereals for test meal 1 and a choice of protein sources for test meal 2. They will be asked to keep to the same choice of cereal and protein source for the repeat meal. They will be asked to consume at least 75% of the meal to ensure the threshold of the glycaemic load is met. The

instructions and details of the test meals are presented in Appendix 11. The control meals will be the participant's usual breakfast of choice.

Participants will be asked to follow their usual insulin regimen as advised by their diabetes team i.e. their usual insulin dose and dose timing. For both test and control meals participants will be asked to avoid any further food intake during three-hour postprandial period other than carbohydrate adjustments required to treat any hypoglycaemia. Participants will also be asked to avoid drinks except water or carbohydrate free juices. They will also be asked to avoid physical activity of more than 30 minutes in duration. To minimise disruption to their normal daily activities, they will be advised to test the meal on a day when there is no planned physical activity i.e. a school day with no morning physical education. The CGM data will be collected throughout this time as discussed above.

Postprandial Questionnaire

The participants will be asked to complete a postprandial questionnaire using 'online survey'. This includes questions about the meal and the three-hour postprandial period. The questionnaire is presented in Appendix 10. They will be asked to wait a minimum of three hours before answering and submitting the questionnaire. They will be encouraged to complete it on the same day as the test or control meal.

Outcome measures

Primary and secondary outcome measures will be based on international guidelines and consensus DiMeglio *et al.* 2018; Battelino *et al.* 2019) of the metrics and target glucose levels to be used in CGM analysis in clinical practice. These are agreed to be:

Metrics:

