- Mean glucose
- Glucose variability (GV) % coefficient of variation (COV) target $\leq 36\%$
- Time in range (TIR) % and time spent between 3.9-10mmol/l
- Time above target (TAR) % and time spent $>10.1\text{-}<13.9\text{mmol/l}$ and $>13.9\text{mmol/l}$
- Time below range (TBR) % and time spent 3.0-3.8mmol/l and $<3\text{mmol/l}$

Target glucose levels:

- TIR - % of readings $>70\%$ or 16hr 48min
- TAR - % of readings $<25\%$ or $<6\text{hr}$ high and $<5\%$ 1hr 12min very high
- TBR- % of readings $<4\%$ or $<1\text{hr}$ low and $<1\%$ or $<15\text{min}$ very low

Primary outcome measure:

- Mean glucose (mmol/l) in the three-hour postprandial breakfast period calculated from the CGM measurements at 5 minutes intervals.

Secondary outcome measures – post prandial period:

- Number and percentage who had pre-prandial glucose in target, mean peak glucose level (mmol/l), mean time to peak (mins), mean time to recover (to pre-prandial levels) (mins) in the three-hour postprandial breakfast period
- TIR, TBR and TAR (% and time) in the three-hour postprandial breakfast period
- Comparisons of the above measurements between cohorts and breakfast test meal compositions.

Data analysis

This will be a mix of univariate, bivariate and multivariate analysis as this is best suited to describing, summarising and visualising these data. Outputs will include the distribution of glucose levels post-breakfast to determine the spread and dispersion of the data.

Safety considerations

Recruitment/consent

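### The Latin square is not specified: it balances meal position but need not balance the preceding meal, which could mix carryover from the cereal meal with the added-protein comparison

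*Combined protocol and SAP*

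**What the plan says.** Under Methodology, Test and control meals, the plan states that "Randomisation will be achieved using a Latin square randomisation" and that "Randomisation will be done in a block of four", and it names a web tool. The text reviewed does not list the sequences, say which Latin square is meant, or say whether a new square is drawn for each block.

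The number of breakfasts to be ordered is described in two ways. The Project summary has three test meals "plus a control meal (usual breakfast), repeating each meal twice in a randomized order using a Latin square randomisation", which is 4 × 2 = 8 breakfasts. Test and control meals says "participants will be randomised to test each of the three test meals on two separate occasions with a control meal (usual breakfast meal) for each" of them. That can be read as pairing a control with every test breakfast, up to 6 + 6 = 12, with only the three test meals placed in random order.

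On content, "test meal two is the same cereal meal with a high glycaemic load (>20) with addition of 10g protein", so meals 1 and 2 differ by the protein alone. On insulin, "Participants will be asked to follow their usual insulin regimen as advised by their diabetes team i.e. their usual insulin dose and dose timing". Data analysis says "This will be a mix of univariate, bivariate and multivariate analysis" and names no sequence, position or previous-meal term.

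**The concern.** A Latin square fixes where each meal falls in the order. It leaves open what each meal comes after. In the cyclic square 1-2-3-C, 2-3-C-1, 3-C-1-2, C-1-2-3, meal 2 comes straight after meal 1 every time it is not first.

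This pair of meals matters because Expected outcomes hopes to learn what added protein does to the glycaemic response, which is the meal 2 minus meal 1 contrast. The two meals share a cereal, are eaten at home, and are taken by families who regularly use CGM. It is plausible that one cereal breakfast affects how the next study breakfast is handled. If so, and if one unfavourable square were reused, much of that change would appear in the protein contrast. A position term would not remove it, because in any Latin square meals are already orthogonal to position.

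**Working it through.** **Inputs.** Four conditions and a block of four come from the Project summary, Sample size, and Test and control meals. The size of any carryover is not in the documents, so results are given per unit of carryover, *c*: the change in mean glucose at the next study breakfast caused by having just had meal 1.

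**The plan's own figure.** The plan gives no figure on sequence balance. Its sample size does reproduce. The noncentrality is N·m·f²/(1 − ρ) = 64 × 4 × 0.15²/(1 − 0.5) = 11.52, with 3 and (64 − 4) × 3 = 180 degrees of freedom, giving power 0.814. The smallest adequate N is 62, and 64 is the next multiple of four.

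**How often a Latin square balances the preceding meal.** All 576 Latin squares of order 4 were enumerated:
- 144 (25%) have every ordered pair of neighbours exactly once.
- 288 (50%) have some meal following one particular meal twice.
- 144 (25%) have some meal following one particular meal three times, that is, whenever it is not first.
- Meal 1 comes directly before meal 2 zero, one, two or three times in 192, 240, 96 and 48 squares. The mean is 1.0.

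**Bias in meal 2 minus meal 1.** Each meal appears equally often in each position and each sequence, so least squares with sequence, position and meal effects reduces to a difference of simple means:

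bias/*c* = (share of meal 2 servings directly after meal 1) − (share of meal 1 servings directly after meal 1).

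The last column is the variance of this contrast with previous-meal terms fitted, divided by its variance without them.

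| Sequence set | Meal 2 after 1 | Meal 1 after 1 | Bias/*c* | Variance ratio |
|---|---|---|---|---|
| Cyclic, one pass | 3/4 | 0 | 0.75 | 5.5 |
| Williams, one pass | 1/4 | 0 | 0.25 | 1.10 |
| Cyclic, same order twice | 7/8 | 0 | 0.875 | 9.2 |
| Williams, same order twice | 2/8 | 0 | 0.25 | 1.11 |
| Williams, second pass reversed | 2/8 | 1/8 | 0.125 | 1.02 |

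The Williams set used is 1-2-C-3, 2-3-1-C, 3-C-2-1, C-1-3-2. Run twice in the same order, it gives predecessor counts of 2 or 3. With the second pass reversed, every ordered pair of different meals occurs exactly twice, and each meal follows itself once, at the turn.

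These fractions assume that only meal 1 carries over. If meals 1 and 2 carry over equally, the Williams biases cancel (0.25 − 0.25, or 0.125 − 0.125), while the cyclic one-pass bias stays at 0.75.

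**In mmol/l, for assumed values of *c*.** One pass, cyclic against Williams:
- *c* = 0.25: 0.19 against 0.06
- *c* = 0.5: 0.375 against 0.125
- *c* = 1.0: 0.75 against 0.25

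**If a fresh random square is drawn per block.** For one random square the bias fraction has mean 0.25 and SD 0.228. Over 22 full blocks (90 = 22 × 4 + 2) the SD is 0.228/√22 = 0.05. The average is then the same 0.25 as a one-pass Williams set, with little spread.

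**Three test meals only.** None of the 12 Latin squares of order 3 balances the preceding meal, so a pair of squares (six sequences) is needed.

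**The case against.** The strongest reply is that the plan contains no error here. A Williams square is itself a Latin square, so the wording already permits it, and nothing says the square is cyclic or reused. Only 48 of 576 squares (8.3%) put meal 1 before meal 2 three times, and redrawing the square for each block would largely settle the matter. This stands: the point concerns an unspecified choice.

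The size of any carryover is also unsupported by a figure. Insulin settings are reviewed before testing, participants keep their usual doses and timing, and closed-loop users are eligible. All of these restrain carryover, though they do not exclude other changes in handling.

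A further objection is that learning persists, whereas the calculation affects only the next study breakfast. Suppose learning of 0.5 mmol/l lasts after the first meal 1, over two consecutive passes. In the cyclic order meal 2 is affected in (3/4 + 1)/2 = 0.875 of servings and meal 1 in (0 + 1)/2 = 0.5, a bias of 0.375 × 0.5 = 0.19 mmol/l. In the Williams set, with meal 1 earlier in two of four sequences, it is (0.75 − 0.5) × 0.5 = 0.125. The gain is smaller, and a previous-meal term would not remove the rest. This also stands.

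Three stronger readings are tempting. A reader might infer that the protein comparison is confounded as planned; the documents do not support that, since the square is not stated. A reader might infer that any change in handling would be credited wholly to the protein; even in the cyclic square one sequence in four has meal 2 before meal 1, and the effects are poorly separated (variance × 5.5), not inseparable. A reader might infer that a Williams square removes carryover; it leaves 0.25 or 0.125 of it unless a previous-meal term is fitted.

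**Conclusion.** The point holds as a low-cost improvement to an unspecified design choice. The named method guarantees balance of position but not of the preceding meal. In the worst case, a reused cyclic square, 0.75 of any next-breakfast carryover from the cereal meal enters the protein contrast (0.875 if the order is repeated), against 0.25 or 0.125 with a Williams set.

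The choice of square also decides whether a previous-meal adjustment is usable: the variance rises 5.5-fold or more in a cyclic square, but by 10% or 2% in a Williams set.

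The conclusion rests on four randomised conditions, carryover to the next study breakfast only, and reuse of one square. The amount of carryover is an assumption throughout.

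**What to change.** 1. Reconcile the Project summary (four meals, each twice, eight breakfasts) with Test and control meals (a control for each test meal), and state how many breakfasts are randomised.
2. If four conditions are each taken twice, list the sequences: in each block of four use 1-2-C-3, 2-3-1-C, 3-C-2-1 and C-1-3-2, with the second pass in reverse order. Each meal then follows each other meal twice per block.
3. If only the three test meals are ordered, use the six-sequence Williams design. The block of four then no longer fits and needs changing.
4. Add a previous-meal term as a sensitivity analysis of mean postprandial glucose, and say that it addresses next-breakfast carryover, not persistent learning.

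For four conditions, the block size, number of breakfasts and N for the main analysis do not change. The sensitivity analysis raises the variance of the contrast by about 2% (10% for a single pass). Because 90 is not a multiple of four and some participants will drop out, the balance achieved will be approximate. If the investigators prefer random squares, stating that a new one is drawn for each block would deal with most of the concern.

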- To determine the variability of glucose excursion, level and peak and the recovery time in the three-hour postprandial period.
- To describe comparisons between all the above measurements and the variables of sex, age, disease duration, BMI, HbA1c, insulin dose/sensitivity and insulin regimen.
- To describe comparisons between all the above measurements and the glycaemic load and composition of the test and control meals.

Study design

This is a quantitative study. Dexcom CGM data will be collected for the period of recording. Participants will be asked to test three breakfast meals on two occasions and submit a postprandial questionnaire after each test meal to confirm it has been tested. The postprandial period will be three hours following the end of the breakfast test meal. The test meal recipes

will be provided by the chief investigator. The dietary composition of the meals has been analysed using the Nutritics dietary analysis programme (Nutritics, 2022). The glycaemic index and load of the meals is estimated from the Nutritics programme which uses available data from the international tables of glycaemic index and glycaemic loads (Atkinson *et al.* 2008; 2021). Most foods were based on average composition across different brands. For the added fibre bread used in test meal 3, an average of three known brands was used calculated by the chief investigator. The meals will be taken in the home environment with the food provided by the families. The participants will be asked to take the test meal on a day when their CGM reading is between 4-10mmol/l and when there has been no nocturnal hypoglycaemia on the night before the planned test. The participants will act as their own control. They will be asked to complete a postprandial questionnaire for control meals as well. The control meals will be their usual breakfast of choice. The study duration, commencing with the recruitment of the first participant and ending when data has been fully described, is anticipated to be two years.

Participants

Eligibility criteria

- Children and young people aged between 5-17 years
- Diagnosis of type 1 diabetes for a minimum of one year
- On multiple daily injections (MDI) together with carbohydrate counting or Continuous Subcutaneous Insulin Infusion (CSII) using either open or closed loop systems.
- Use Dexcom continuous glucose monitoring (CGM) on a regular basis
- Have a Dexcom Clarity account and use the Clarity App

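### Meal order is randomised but families choose the morning; if that choice depends on which meal is next, the comparisons between meals can be biased

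*Combined protocol and SAP*

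**What the plan says.** The Project summary has participants "repeating each meal twice in a randomized order using a Latin square randomisation". Under Methodology, Test and control meals, the plan repeats "Randomisation will be achieved using a Latin square randomisation" and adds "Randomisation will be done in a block of four". What is allocated is a sequence. No date, interval or scheduling rule appears.

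The choice of morning is left to the participant, subject to conditions:

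- Study design: "The participants will be asked to take the test meal on a day when their CGM reading is between 4-10mmol/l", after a night without hypoglycaemia.
- Test and control meals: "they will be advised to test the meal on a day when there is no planned physical activity". Safety considerations gives a similar rule on planned exercise.

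On who prepares the meal, Study design says "The meals will be taken in the home environment with the food provided by the families". No blinding is described.

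Under Outcome measures, the primary outcome is the absolute mean CGM glucose over the three hours after breakfast, not the change from the pre-meal value. Data analysis names no model and no adjustment for pre-meal glucose or type of day.

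**The concern.** A randomised order protects a crossover comparison only if the conditions under which each meal is eaten are unrelated to which meal it is. Here a family that buys and prepares the food will ordinarily know the next meal. It can also see the morning's glucose before deciding to go ahead or wait. It can obey every stated rule and still hold one meal for a lower or steadier morning while taking another on any morning that qualifies. The pairing of meal with morning is then no longer random.

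Starting glucose feeds directly into an absolute three-hour mean, so the contrasts could shift before anyone has eaten and with every questionnaire returned. These contrasts matter. The objectives compare outcomes by glycaemic load and meal composition, the sample size is built on a within-participant comparison of four meals, and Expected outcomes looks for evidence on glycaemic load and added protein.

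**Working it through.** **1. The plan's own figure.** Inputs from Sample size: f = 0.15, four measurements, correlation 0.5, alpha 0.05, power 0.80. For the within-participant factor, λ = n·m·f²/(1−ρ), with m−1 and (n−1)(m−1) degrees of freedom. At n = 64, λ = 64 × 4 × 0.0225/0.5 = 11.52 on 3 and 189 df, which gives power 0.81. The smallest n reaching 0.80 is 62, and rounding up to a multiple of four gives 64. The stated figure reproduces.

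**2. The size of effect the plan looks for.** f = 0.15 corresponds to a gap between meals of 0.30 SD (meals split two and two), 0.35 SD (one meal differs) or 0.42 SD (two extremes, the others midway). At an assumed SD of 3 mmol/l, the first of these is 0.30 × 3 = 0.9 mmol/l.

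**3. Assumptions for the illustration (none is in the document).**

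- Pre-meal glucose is uniform over the permitted 4-10 mmol/l, mean 7.0.
- Some families wait for 7 or below before meals 1 and 2, so the start is uniform over 4-7, mean 5.5. They take meal 3 on any qualifying morning. The start gap is 7.0 − 5.5 = 1.5 mmol/l.
- A fraction of that gap carries into the three-hour mean: 0.25, 0.5 or 0.8.
- The SD of the outcome is 3 mmol/l, and the plan's correlation of 0.5 applies.

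**4. Bias in meal 3 v meal 1.** Bias b = share of families × 1.5 × carry-over. For example, 0.25 × 1.5 × 0.8 = 0.30 mmol/l.

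**5. False positives with no true meal effect, three test meals only.** With meals 1 and 2 both shifted by b, f = b√2/(3·SD). Then λ = 64 × 3 × f²/0.5 on 2 and 126 df. For b = 0.30, f = 0.047 and λ = 0.85, giving a rejection rate of 11.8%.

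| Families | Carry-over | Bias, mmol/l | False-positive rate |
|---|---|---|---|
| 10% | 0.25 | 0.04 | 5.1% |
| 10% | 0.5 | 0.08 | 5.4% |
| 10% | 0.8 | 0.12 | 6.0% |
| 25% | 0.25 | 0.09 | 5.6% |
| 25% | 0.5 | 0.19 | 7.5% |
| 25% | 0.8 | 0.30 | 11.8% |
| 50% | 0.25 | 0.19 | 7.5% |
| 50% | 0.5 | 0.38 | 16% |
| 50% | 0.8 | 0.60 | 35% |

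If timing ignores which meal is next, b = 0 and the rate stays at 5%.

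**6. What this does not cover.** Meals 1 and 2 are treated alike, so the bias in the protein contrast (2 v 1) is exactly zero here. It would arise only if families treated those two meals differently. The control is left out for two reasons. The 4-10 mmol/l condition is worded for the test meal. The control's place in the square is also unclear: the summary has four meals twice each, whereas Methodology says "test each of the three test meals on two separate occasions with a control meal (usual breakfast meal) for each test meal".

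**The case against.** **Bias needs meal-dependent timing.** This stands. Equal day-picking for every meal affects whom and what the results describe, not the contrasts, and nothing in the document shows that families wait for particular meals. A reader might infer that free choice of day undoes the randomisation. That is a worst case the text does not establish.

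**The direction is unknown.** This also stands. A reader might infer that families would save better mornings for the high-load cereal and so hide its effect. The document describes the meals as ones children like and commonly eat, and says nothing about families fearing one of them. The bias could go either way.

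**Carry-over may be small.** Children follow their usual insulin regimen and some use closed-loop pumps. The low end of the range allows for this, and at 0.25 the effect is slight unless many families are involved.

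**Safeguards exist, and others may be unseen.** The day conditions narrow the choice, CGM records the starting value, and pre-prandial glucose in target is a secondary outcome. But a window 6 mmol/l wide remains, and a descriptive count corrects nothing. A scheduling rule in Appendix 11 cannot be excluded. If there is one, stating it in the main text would largely settle the point.

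**The aim is descriptive.** The stated aim is, but the objectives, sample size and expected outcomes all rest on comparing meals.

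**Conclusion.** The point holds as a gap in concealment. The order is random, but an unblinded family chooses the morning and nothing in the available text separates that choice from the next meal. That the family knows the next meal is inferred from its supplying the food at home.

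Under the stated assumptions the bias in meal 3 v meal 1 is negligible if a tenth of families are involved (at most 0.12 mmol/l). At a quarter it reaches up to a third of the 0.9 mmol/l planning effect (0.30/0.9), and at a half up to two thirds (0.60/0.9). These are illustrations, not estimates. The result depends strongly on the share of families and on carry-over, and the document informs neither.

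The point is worth fixing before data collection because analysis can correct only the part carried by measured variables. Glucose trend and the night before would remain unless they too were modelled. The stated sample size of 64 is not affected.

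**What to change.** In Methodology, Test and control meals, add that on a chosen morning the family completes a short form on the Online Surveys platform already in use, confirming that the existing day conditions are met. Only then is it shown the next meal in its allocated order. The form's timestamp records the commitment. The day conditions themselves do not change.

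From data already collected, prespecify three checks:

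1. Compare the order eaten with the order allocated. This finds departures from sequence, though not waiting within it.
2. Tabulate pre-meal CGM glucose and day type by meal.
3. Repeat the meal comparison adjusting for pre-meal glucose, stating that this removes only the measured part of any selection.

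Two additions may look attractive but should not be made: counting the qualifying mornings a family passed over, and restricting an analysis to first qualifying mornings. Questionnaires cover only study breakfasts, so planned activity on other mornings is not recorded. The restricted analysis would also select on behaviour after randomisation.

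The cost is a few lines in the protocol and participant instructions, one short extra form per study breakfast, and a small amount of analysis. Families would need to keep ingredients for the remaining meals at home; the plan describes these as common and affordable. No extra participants or visits are needed.
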